3.2.1 Serum nicotine concentration

At each experimental session, participants will be negative for urine cotinine (urine dipstick – detection threshold of 50 ng/ml – NarcoCheck[©])²³ and concentration of serum nicotine should be below 2 ng/ml, a value confirming the status of nicotine free vaping and the lack of significant nicotine exposure.^{24,27} Serum nicotine will be measured by means of a mass spectrometer with a jet stream electrospray ion source.

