1.3. Study of acute nicotine free vaping effects on arterial O₂ concentration (2017-2018)

At our knowledge, we are the first to demonstrate that acute high wattage PG/GLY vaping induces transcutaneous hypoxia. Transcutaneous hypoxia has been described with tobacco smoking, as a consequence of nicotine-induced vasoconstriction,⁹ but effects of a nicotine free PG/GLY liquid vaporization on this parameter were unknown. Tissue oxygen (O₂) and CO₂ tensions reflect the delivery of O₂ and the extraction of CO₂, which are both dependent on respiratory and microcirculatory functions.¹⁰ The decrease in underlying dermal O₂ levels could be explained by: 1) a decrease in arterial O₂ concentration; 2) changes in hemodynamic parameters; and/or 3) microcirculatory endothelial dysfunction.¹⁰ Our current experiments are focusing on acute effects of PG/GLY vaping on arterial O₂ concentration, namely, concentration of hemoglobin, O₂ saturation of hemoglobin and its biological determinants and arterial O₂ partial pressure.¹¹⁻²

1.4. Studying the reversibility of PG/GLY aerosol effects on lungs in regular e-cigarettes users

Our new working hypothesis is that high temperature vaping deposits a hot and moist large amount nanoparticulate PG/GLY aerosol deeply in the lungs,¹³ resulting in small airways inflammation and constriction,¹³ rheological surfactant and mucus properties disturbances,¹⁴ small bronchioles and alveoli collapses,¹⁴ arterial oxygenation impairments, which decrease hemoglobin-oxygen saturation and induce the tissue hypoxia we observed.¹⁰

In order to verify the new hypotheses aforementioned on PG/GLY vaping induced-lung gas exchanges perturbations and its reversibility, as well as to disentangle respective effects of PG/GLY and nicotine, we will test effects of vaping cessation in regular e-cigarettes users by means of classical cardiorespiratory parameters assessments,¹⁷⁻¹⁹ lung function tests with diffusing capacity analysis and a maximal cycle ergospirometer test.²⁰ Lastly, quantitative discovery serum proteomics²¹ and metabolomics²² in the serum, urine and exhaled breath

condensate will be performed with the view to highlight biomarkers associated with chronic high wattage vaping exposition.

2. Goals of the research

This research proposal tests the following hypothesis regarding the reversibility of PG/GLY and PG/GLY plus nicotine vaping in regular e-cigarettes users

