A. In comparison to pursuit of PG/GLY vaping with or without nicotine, e-cigarette cessation for five days:

- Increases transcutaneous O₂ tension and O₂-haemoglobin saturation
- Decreases respiratory rhythm
- Increases lung diffusing capacities and forced expiratory flows
- Increases maximal rate of oxygen consumption during cycle ergospirometer test
- Modifies heart rate variability
- Decreases arterial stiffness
- Decreases serum PG/GLY and nicotine concentrations

B. In comparison to PG/GLY vaping with nicotine, e-cigarette cessation for five days or PG/GLY vaping:

- Increase cutaneous vascular conductance and decrease arterial stiffness
- Increase acetylcholine and heat mediated vasodilation

C. Each of the three experimental sessions (e-cigarette cessation, PG/GLY vaping and pursuit regular consumptions):

- Induces specific serum, urine and exhaled breath condensate metabolomics profiles
- Induces specific serum proteomics profile

This research proposal tests also the following hypothesis regarding acute effects of PG/GLY vaping with and without nicotine in regular e-cigarettes users:

A. In comparison to baseline, PG/GLY vaping without nicotine:

- Decreases transcutaneous O₂ tension and O₂-haemoglobin saturation
- Increases respiratory rhythm
- Increases serum PG/GLY concentrations
- Induces specific serum, urine and exhaled breath condensate metabolomics profiles

B. In comparison to baseline and PG/GLY without nicotine, PG/GLY vaping with nicotine:

- Decreases transcutaneous O₂ tension and O₂-haemoglobin saturation
- Decrease continuous vascular conductance and increase arterial stiffness
- Increases respiratory rhythm
- Increases serum PG/GLY and nicotine concentrations
- Induces specific serum, urine and exhaled breath condensate metabolomics profiles

3. Methodology

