3.1. Participants, interventions, periods and randomization

The participants, who are exclusive vapers since at least one years, will undergo three experimental periods in a random order: e-cigarettes cessation for five days (**cessation session**), nicotine free vaping for five days (**nicotine free session**), regular e-cigarettes consumption (**regular consumption session**). Baseline clinical cardiorespiratory parameters will be assessed at the start of each of the 3 experimental sessions. The participants will, then, vape sham-puffs (**cessation session**), nicotine free-puffs (**nicotine free session**) and

nicotine puffs (**regular consumption session**). During acute exposition, we will monitor at each puff any feelings of throat irritation, burn taste and Borg perception scale items (cough, chest tightness, breathlessness, secretions and wheezing). This acute exposition will be followed by clinical cardiorespiratory parameters assessment, lung function tests and maximal cycle ergometer test.

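### Section 3.2.1 applies a nicotine-free criterion to every session, which contradicts the nicotine puffs assigned at the regular consumption session

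*Combined protocol and SAP*

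**What the plan says.** All references are to the combined protocol and SAP.

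- **Section 3.2.1** sets the criterion: "At each experimental session, participants will be negative for urine cotinine" (dipstick threshold 50 ng/ml), and "concentration of serum nicotine should be below 2 ng/ml, a value confirming the status of nicotine free vaping" and "the lack of significant nicotine exposure". It names no sampling time and excepts no session.
- **Section 2** (item C of the reversibility hypotheses) counts regular consumption as one of the three experimental sessions.
- **Section 3.1** gives each session its acute exposure: sham puffs, nicotine free puffs and, last, "nicotine puffs (regular consumption session").
- **Section 2** also states the expected direction. Cessation, compared with continued vaping, "Decreases serum PG/GLY and nicotine concentrations" (reversibility, A). Vaping with nicotine, compared with baseline and with nicotine free vaping, "Increases serum PG/GLY and nicotine concentrations" (acute, B).
- **Section 1.4** gives as one aim "to disentangle respective effects of PG/GLY and nicotine".
- **Section 3.2** takes blood at baseline and 1 hour after exposure in every session, assays all of it for nicotine, PG and GLY as a compliance check, and then says that a protocol violation ends participation and removes all of the participant's data.
- **Section 3.3.8** has urine collected one hour before and 100 minutes after exposure.

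**The concern.** A session cannot both deliver the nicotine exposure under study and be certified as free of it. Section 3.2.1 uses the limit as evidence that no meaningful nicotine exposure took place, and by its wording it asks for that evidence at the session where nicotine is the assigned exposure.

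Two things are at stake. The first is retention: section 3.2.1 sits under the compliance heading of 3.2, so a breach would naturally be read as a violation that removes the whole participant. The session order is random, so the cessation data would be either already collected and then removed, or never collected. The second is the exposure contrast: a participant who does meet the limit at the regular consumption session gives no evidence there of the continued nicotine use that cessation and nicotine free vaping are compared with.

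**Working it through.** The contradiction is textual. The arithmetic only shows how much room the plan has.

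**1. The criterion under each possible scope**

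| Scope of the 3.2.1 criterion | Participant above the limit at the regular session | Participant below the limit at the regular session |
|---|---|---|
| All sessions, all blood samples (literal text of 3.2.1 read with 3.2) | Fails a compliance check by taking the puffs that 3.1 assigns; 3.2 implies removal of all data | Covered values lie from 0 to below 2 ng/ml, so any two sessions differ by less than 2 − 0 = 2 ng/ml; the nicotine contrasts in section 2 lack exposure |
| All sessions, pre-exposure samples only | Fails by continuing the regular nicotine use that the session is meant to represent | Acute contrasts can survive, because the puffs follow the check; the five-day comparisons with regular nicotine vaping lack evidence of continued use |
| Cessation and nicotine free sessions only | No conflict | No conflict |

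Only the last row agrees with sections 2 and 3.1, and the text does not state it.

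**2. Samples caught by the literal wording**

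Inputs: 2 blood draws per session (3.2, 3.3.8), 3 sessions (3.1), 21 enrolled (3.3.13), all assumed to attend every session.

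- Total: 2 × 3 × 21 = 126 blood samples.
- Regular consumption session: 2 × 21 = 42, and 42/126 = one third.
- Drawn after the nicotine puffs: 1 × 21 = 21.

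These are design counts, not a measure of loss. No count is given for urine, because nothing says which of the 3.3.8 specimens the dipstick is run on.

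**3. The reserve against discards**

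Inputs from 3.3.13: SD 7 mm Hg, difference 10 mm Hg, power 80%, two-sided alpha 0.05, 16 needed, 21 enrolled.

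- The plan's 16 is reproduced by the normal approximation for two independent groups: n per group = 2 × (1.960 + 0.842)² × 7² / 10² = 7.69, rounded up to 8, so 16 in total (power 0.815).
- Reserve: 21 − 16 = 5, and 5/21 = 23.8%.

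This reserve is relative to the plan's own 16. Each participant attends all sessions. A paired t-test with SD 7 per measurement would need 10, 8, 7 or 5 participants at assumed within-person correlations of 0, 0.25, 0.5 or 0.75. So 16 is not a hard floor, and how the sample size was derived is a separate matter.

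**4. Illustration under assumed discard rates**

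The documents give no rate. Let f be an assumed probability that a participant is discarded, and let the number kept follow Binomial(21, 1 − f).

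| f (assumed) | Expected kept, 21 × (1 − f) | P(at least 16 kept) |
|---|---|---|
| 0.10 | 18.9 | 0.986 |
| 0.25 | 15.75 | 0.567 |
| 0.50 | 10.5 | 0.013 |

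This shows only how the reserve of 5 behaves. It does not predict the loss.

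**The case against.** **The intent is plain.** The rationale speaks of nicotine free vaping, so a sensible reader would apply the limit to the cessation and nicotine free sessions only. That is probably right, and it lowers the severity. It does not remove the error: section 3.2.2, the next section, names the sessions it uses for PG and GLY, whereas 3.2.1 says each session.

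**Only the pre-exposure sample may be meant.** The text neither says this nor excludes it. Section 3.2 tests all blood samples, and section 3.3.5 shows that the protocol states a start-of-session timing when it wants one. The twelve hours in 3.2 refer to fasting; no abstinence from vaping is stated. Part of the objection stands, however: on this reading a participant can pass and then take the puffs, so the acute contrasts keep their exposure. A reader might infer that the rule defeats every nicotine comparison however it is applied. The documents do not support that.

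**Regular use may be nicotine free for some.** Section 2 does mention vaping with or without nicotine, but section 3.1 assigns nicotine puffs to the regular consumption session without exception.

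**The discard link is already there.** This largely stands. Section 3.2 says that the assays confirm compliance and then gives the discard rule, so a failed assay is naturally read as a violation. Stating the link, and naming the deciding samples, are clarifications rather than further defects.

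**Conclusion.** The criterion in 3.2.1 contradicts sections 2 and 3.1 and should be corrected. The conclusion rests on the wording alone: the criterion covers every session, one session is assigned nicotine, and no section makes an exception.

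The consequence depends on two things that the text leaves open or only implies: which samples count, and that exceeding the limit is a violation. If all blood samples count, participants who follow their assignment can lose their whole dataset. If only pre-exposure samples count, the damage is confined to the five-day comparisons of cessation or nicotine free vaping with regular nicotine vaping. If the two nicotine-free sessions alone were meant, the regular consumption session costs no data.

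A reader might infer that all 21 datasets would be lost. That needs every participant to exceed the limit at the regular consumption session and every exceedance to be enforced as a violation. The documents give no failure rate, and the stated rationale makes such enforcement unlikely. The loss therefore cannot be quantified; the supported figure is the plan's reserve of 5 participants out of 21.

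This should be fixed before compliance is judged. Otherwise, whose data are removed would rest on an after-the-fact reading of the rule.

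**What to change.** Reconcile sections 3.1, 3.2 and 3.2.1.

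1. If the sponsor confirms that this is the intent, replace the opening words of 3.2.1 with *At the cessation and nicotine free sessions*.
2. On the same condition, state that nicotine or cotinine above the limit at the regular consumption session is not a protocol violation under 3.2.
3. As a clarification, name the samples that the criterion applies to: baseline serum, 1-hour serum or both, and which urine specimen. The documents give no detection window for either marker, so the sponsor should say what period each chosen sample is taken to verify.
4. As a clarification, confirm that failing the criterion at the cessation or nicotine free session is a violation that triggers the discard rule.

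The cost is one changed phrase and about three sentences. Nicotine is still measured in all sessions as 3.2 plans, and no new data, assays or visits are needed.

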3.2.2 Serum propylene glycol and glycerol

Since serum PG and GLY normal values in regular vapers are unknown, we will take means of PG and GLY serum concentration measured during the **regular consumption session**

and nicotine free session for further comparison to the value obtained during the **cessation session**, in order to confirm the compliance to the study protocol. Serum values of PG and GLY will be assessed using gas chromatography with a flame ionization detector.²⁵

3.3 Project plan and various step

The 5h-sessions will take place in the morning at the Hôpital Erasme. During each session, participants will be tested before and after acute exposure at the Cardiology Laboratory (ULB – Pr. [name]) for: 1) noninvasive continuous hemodynamic parameters (Electrocardiogram monitoring (AdInstrument[®]) and a beat-to-beat hemodynamic monitoring system¹⁷ Finapres Medical Systems[®]) 2) continuous respiratory rhythm, end-tidal carbon dioxide and blood oxygen saturation (Capnostream[®]);²⁸ 3) transcutaneous oxygen and carbon dioxide partial pressures (Perimed[®]);¹⁰ 4) skin microcirculatory blood flow by means of laser Doppler perfusion monitoring (continuous vascular conductance, heat test, acetylcholine and sodium nipride iontophoresis) (Perimed[®]);¹⁸ 5) Fractional exhaled carbon monoxide will be assessed at the start of each experimental session using a Smokerlyzer (SineFuma[®], Breda, Holland); 6) arterial stiffness indices (Sphygmocor[®]);²⁹ 7) exhaled breath condensate (Viasys Ecoscreen[®]);¹⁹ 8) Urine and 9) venous blood sample. Then, the participants will be directed to the Laboratory of Exercise Physiology, Faculty of Motor Sciences (ULB – Pr. [name]) to perform assessment of: 10) lung function tests plus capillary and membranous lung diffusing capacity as well as maximal ergometer cycle test²⁰ (details in appendix) (figure 2). After completion of clinical study in all participants, biological samples will undergo proteomics²¹ (ULB – Pr. [name]) and metabolomics²² (UMons – Pr. [name]) analysis (details in appendix).

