3.3.2 Continuous respiratory rhythm, end-tidal carbon dioxide and blood oxygen saturation

Continuous, non-invasive, real-time respiratory status monitoring of end-tidal CO₂ pressure, O₂ saturation in arterial blood, respiration rate, and pulse rate will be assessed with the Capnostream 35 monitor[©] (Oridion Medical Ltd, Jerusalem, Israël) throughout all the experimental sessions duration.

3.3.3 transcutaneous oxygen and carbon dioxide partial pressures

A PeriFlux system 5000 (Perimed[©], Järfälla, Sweden) will explore transcutaneous oxygen (O₂) and carbon dioxide (CO₂) partial pressures by means of a PF 5040 unit and a dual transcutaneous O₂ and CO₂ partial pressures E5280 electrode. After wiping the area with alcohol, a TC 550 fixation ring (Perimed[©], Järfälla, Sweden) will be applied to the skin in the medial side of the right arm (lower third and 5 cm distal to the antecubital fossa) at the level of the heart. Four drops of contact liquid (TC 560, Perimed[©], Järfälla, Sweden) will be instilled

inside the TC 550 fixation ring. Avoiding superficial vessels and body hair, the electrode will be placed at the same location for each of the two sessions on the basis of multiples pictures taken during the experimental session. Transcutaneous O₂ and CO₂ partial pressures values will be considered stable when variations did not exceed ± 2 mmHg within 1 min. Electrode remembranring will be done every two sessions.

3.3.4 skin microcirculatory blood flow by means of laser Doppler perfusion monitoring

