3.3.10 Maximal ergometer cycle test

“The sessions will consist of an incremental exercise test on a cycle ergometer to determine $\dot{V}_{O_2\max}$. Initial workload will be set at 35 W and workload will increase by 15 W with each 1 min stage until volitional fatigue. Breath by breath data will be collected and analysed every 5 s using a metabolic system that will be calibrated with room air and standardized gas. The slope of ventilation relative to carbon dioxide production (\dot{V}_E/\dot{V}_{CO_2}) will be calculated with values from rest to maximal exercise. $\dot{V}_{O_2\max}$ will be considered to be achieved when two of the following criteria will be met: an increase in oxygen consumption of less than 100 ml min⁻¹ with a further increase in workload, respiratory exchange ratio (RER) greater than 1.1 or achievement of age-predicted maximal heart rate. Pulse oximetry oxygen saturation (S_{PO_2}) will be continuously monitored with a finger pulse oximeter.” [Med Sci Sports Exerc. 2017 Oct;49\(10\):2131-2138.](#)

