3.3.13 Sample size calculation

The primary objective of this study is to determine whether e-cigarette vaping cessation for five days increases transcutaneous oxygen partial pressure in regular users. Based on our previous researches, we assume that baseline mean transcutaneous oxygen partial pressure will be 80 mm Hg with a standard deviation of 7 mm Hg. To demonstrate that e-cigarette vaping cessation for five days significantly increases transcutaneous oxygen partial pressure, we assume a minimal rise in transcutaneous oxygen partial pressure of 10 mm Hg. We will need 16 patients, with 80% power to detect a group difference of 10 mm Hg in the change of transcutaneous oxygen partial pressure at a two-sided alpha-level of 0.05. We will enroll 21

participants in order to be sure to achieve a sufficient statistical power.

4. References

5. Etter JF. Throat hit in users of the electronic cigarette: An exploratory study. *Psychol Addict Behav*. 2016;30:93-100
7. Marseglia GL, Cirillo I, Vizzaccaro A, Klersy C, Tosca MA, La Rosa M, Marseglia A, Licari A, Leone M, Ciprandi G. Role of forced expiratory flow at 25-75% as an early

marker of small airways impairment in subjects with allergic rhinitis. *Allergy Asthma Proc.* 2007;28:74-8

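### No masking of operators, readers or testers is described, and the primary transcutaneous value has a stability rule but no fixed window, summary or masked reader

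*Combined protocol and SAP*

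**What the plan says.** All references are to the combined protocol and SAP.

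- **Design (section 3.1).** Each participant has three sessions in random order: five days of cessation, five days of nicotine-free vaping, and regular consumption. Sham puffs are used in the cessation session. The text does not say from whom the session is concealed, if from anyone.
- **Hypotheses (section 2).** Most physiological hypotheses have a direction. Cessation is expected to raise transcutaneous oxygen tension, forced expiratory flows and maximal oxygen consumption, for example. Heart rate variability and the metabolomic and proteomic profiles have no stated direction.
- **Primary measurement (section 3.3.3).** The only reading rule is that "partial pressures values will be considered stable when variations did not exceed" ±2 mm Hg within 1 minute. Which stable minute counts, how it is summarised and who takes the value are not stated.
- **Second laboratory (sections 3.3 and 3.3.10).** After the cardiology measurements, "Then, the participants will be directed to the Laboratory of Exercise Physiology" for lung function, diffusing capacity and the cycle test. In that test "workload will increase by 15 W with each 1 min stage until volitional fatigue", and maximal oxygen uptake is accepted when two of three criteria are met.
- **Sample size (section 3.3.13).** The baseline mean "will be 80 mm Hg with a standard deviation of 7 mm Hg", and "we assume a minimal rise in transcutaneous oxygen partial pressure of 10 mm Hg". The result is "We will need 16 patients, with 80% power to detect a group difference of 10 mm Hg", "at a two-sided alpha-level of 0.05". Enrolment is set higher: "We will enroll 21".

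**The concern.** Random order balances period effects on average. It does not stop someone who knows the session from reading or encouraging towards the expected result.

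Two routes are open under the plan as written:

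1. **The primary value.** Sessions last five hours, and several minutes before or after exposure could meet the stability rule. With no fixed window or summary, the choice among them could be made with the session known.
2. **The effort-dependent tests.** Forced expiratory flows and maximal oxygen uptake depend partly on how the participant is encouraged. The laboratory that runs these tests is not stated to be unaware of the session.

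At stake is a systematic shift in the primary outcome and in some secondary outcomes. Larger numbers do not average such a shift away.

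**Working it through.** **1. The plan's own figure.** Inputs from section 3.3.13: difference 10 mm Hg, SD 7 mm Hg, power 80%, two-sided alpha 0.05.

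- Two independent groups, normal approximation: n per group = 2 × ((1.960 + 0.842) × 7/10)² = 7.7, so 8 per group and 16 in total.
- Paired comparison of changes, four independent readings each with SD 7: SD = 7 × √4 = 14, and n = ((1.960 + 0.842) × 14/10)² = 15.4, so 16.

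The stated 16 reproduces by either route (18 with t-based versions). Masking does not alter it, so there is no corrected sample size.

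**2. What a systematic shift would do (illustration only).** The documents give neither the size of any reading bias nor the SD of a within-person difference, and the visible text names no test. My assumptions are:

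- a paired t test with no true effect;
- a net shift b of 1, 2 or 4 mm Hg in the paired difference;
- SD of the paired difference = 7 × √(2(1 − ρ)) for levels, which is 9.9 at ρ = 0 and 7 at ρ = 0.5; and 14 for a difference of changes, as in step 1.

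The noncentrality is b × √n / SD. The error rate is the probability that a noncentral t variable with n − 1 degrees of freedom falls outside the two-sided 5% limits.

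For n = 16 and b = 2, the noncentrality is 2 × 4/9.9 = 0.81 at SD 9.9, 2 × 4/14 = 0.57 at SD 14, and 2 × 4/7 = 1.14 at SD 7.

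| n | SD of paired difference | b = 1 | b = 2 | b = 4 |
|---|---|---|---|---|
| 16 | 7 | 8.3% | 18.8% | 57.1% |
| 16 | 9.9 | 6.7% | 11.8% | 32.8% |
| 16 | 14 | 5.8% | 8.3% | 18.8% |
| 21 | 7 | 9.6% | 23.9% | 70.2% |
| 21 | 9.9 | 7.3% | 14.3% | 42.2% |
| 21 | 14 | 6.1% | 9.6% | 23.9% |

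The error rises from 16 to 21 participants because a fixed bias becomes easier to detect as precision improves.

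**3. The effort-dependent tests.** No arithmetic is offered. The documents give no figure for oxygen uptake per watt or for the expected maximum, so an extra 15 W stage cannot be converted into a bias.

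**The case against.** The strongest reply is that silence is not evidence of absence. An opening part of the document, the appendix and figure 2 were not in the text supplied for review, and masking may be described there. The primary signal comes from an instrument with a numerical stability rule, and no reader is named. The skin-flow recordings have fixed durations: 20 minutes for each iontophoresis curve and 20 minutes of heating. The exercise test has partly objective criteria for maximal effort. And participants know whether they stopped vaping, so masking the testers cannot remove bias from their own effort.

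Most of this stands, and it rules out several stronger readings that a reader might infer:

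- **That nobody is masked.** The text supports only that no masking is described.
- **That a reader picks the primary value, or that traces are stored and segments chosen off line.** These are inferences. Continuous recording is stated for haemodynamics, respiration and skin flow. For the transcutaneous signal, the text gives only the stability rule.
- **That the ±2 mm Hg band implies a bias of 2 to 4 mm Hg, or 20% to 40% of the target.** The band describes variation within one minute. It neither bounds nor estimates how far one eligible minute differs from another.
- **That every outcome could be pushed in a hypothesised direction.** Heart rate variability and the omics profiles have none.
- **That an extra cycle stage shows the size of the bias in maximal oxygen uptake.** This needs figures the documents lack. Where the plateau criterion is met, a further stage adds less than 100 ml/min.

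The gap itself remains: the text fixes no window or summary for the primary value, and says of no operator, reader, analyst or laboratory that the session is withheld from them.

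**Conclusion.** The point holds as a cheap improvement to trial conduct. As the visible text stands, the primary value could be selected, and the effort-dependent tests encouraged, with the session known.

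The size of any resulting bias is unknown. On the assumptions above, a net 2 mm Hg shift would take the 5% error to about 12% with 16 participants (8% to 19% over SDs of 14 to 7), and to about 14% with 21 (10% to 24%). These figures show sensitivity to a hypothetical shift and do not estimate one. The sample size is unaffected.

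If masking is already planned in a part not supplied, stating it takes a sentence, but the window and summary for the primary value still have to be fixed.

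**What to change.** Before data collection, because encouragement cannot be corrected afterwards:

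1. Pre-specify the transcutaneous oxygen window and summary, for example the mean over a fixed interval before and after exposure, with the stability rule as a quality check.
2. Export the continuous recordings under a code without the session name, and extract the values before the code is opened. If the transcutaneous signal is not currently saved, save it.
3. Do not tell the exercise laboratory which session it is, ask participants not to disclose it, and use a fixed encouragement script for lung function and the cycle test.
4. State in the protocol who is and is not masked.
5. Acknowledge the participant's own knowledge of the session when interpreting effort-dependent outcomes.

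The cost is some file coding and an instruction to the second laboratory, with no added visit, procedure or participant. Masking of testers will be imperfect where participants reveal their session.
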